## **SECONDARY OUTCOME:**

3. Daily prospective ratings of Sleep Problems (0-4) and Anxiety (0-4) evaluated from prospective Calendar ratings as a daily average during the final 28 days of therapy with average run-in scores as covariates.

As additional assessments of health, participants will complete the following questionnaires:

*Personal Health Questionnaire – 9 (PHQ-9)* is a standardized questionnaire administered as a screening tool for depression . A score of 15 or higher represents moderately severe depression and is the point at which treatment is recommended. Women with PHQ-9 scores  $\geq 15$  will be assessed on a case-by-case basis. Women will be excluded if assessed as needing treatment and/or further investigation for depression. Also, region-specific contact information for mental health resources will be provided. Women suspected of being suicidal will be advised to go to the nearest emergency department and emergency services will be deployed as appropriate. The PHQ-9 will be completed at the randomization and final visits.

*CeMCOR Perimenopause Interference Questionnaire* (attached).

We have recently developed and validated this two-item, self-administered visual analog scale to assess the extent to which the body and mood changes of perimenopause interfere with a woman's usual activities. The two items are averaged to provide a single 100-point score. In a recent validation study ([name] & [name], unpublished MS), we showed fair test-retest repeatability over a 1-2 month period ( $R=0.51$ ,  $n=42$ ), as well as a good correlation with the Vitality Scale of the SF-36 HRQoL instrument ( $R=0.59$ ,  $n=62$ ). Using the interpersonal comparison method of Redelmeier , we estimate that the minimal important difference in the CeMCOR-PIQ is 17. The CeMCOR-PIQ will be completed at the initial, randomization and final visits.

## **2.9 Measurement of outcome measures at follow up**

The study timeline for each subject is shown on the following page. Women will complete the Diary or Calendar throughout the study. Questionnaires will be completed at the initial, randomization and final visits.

## **2.10 Relevance to health care service**

No formal health economic analysis is planned. The costs of the proposed intervention are modest (as compared with, e.g., surgery) and a complete health economic analysis would require data collection well beyond the scope of the study.

[figure not shown]
## **2.11 Sample size**

The **proposed sample size is 175 women**, to be stratified into Early and Late Perimenopause and randomized equally to active therapy or placebo. Previous analysis of similar VMS Score data from menopausal breast cancer therapy studies  concluded that a VMS Score difference of 3 is clinically important, which supports our recent estimate of 2.7 for the minimal important difference in perimenopausal women using the interpersonal assessment methods of Redelmeier  ([name] & [name], unpublished MS). This corresponds to an effect size of 0.58 . We anticipate more VMS variability in perimenopause than in postmenopause, and thus a smaller effect size. The sample size of 175 reflects an anticipated discontinuation rate of 20% (as in our past progesterone trial for VMS in postmenopausal women), and an effect size of 0.48 (revised to allow for 20% greater SD in perimenopausal women above that in postmenopause), an alpha of 0.05 using a two-tailed test and having a power of 0.80 to detect a significant difference between two groups (calculations using GPower3).

## **2.12 Recruitment—rate, organization, evidence it is achievable**

Given our previous recruitment success, we anticipate that many perimenopausal women will be interested in participating. Each woman's participation will take 112 days (timeline below).

**Figure 3: Flow of Participants through the Trial.**

We plan a three-year continuous recruitment period, with a gradual increase in recruitment during this time as word-of-mouth increases (see **Gantt chart** in appendices). We will allow extension of this recruitment period if enrollment targets are not met and funds allow. We project enrollments of 20, 60, 75 and 20 women during the four years of the study (Year 1 includes 6 months of recruitment; Year 4 includes two months of recruitment and 4 months to allow completion of the study by the last participants) with an anticipated six women enquiring about participation for each eligible and enrolled participant (based on our pilot research experience).

Our past recruitment experience has shown that broadcast emails at a local health authority, posting notices on library and community boards, advertising on the CeMCOR web page and newsletter, and free public lectures on perimenopause will all be effective. We will, of necessity, include more internet and social media-based as well as cross-Canada women's health and perimenopausal contacts to aid recruitment. For our recently completed randomized trial for postmenopausal women, we enrolled 178 postmenopausal women with VMS, using more stringent screening conditions (e.g., non-smoking, normal body weight, no history of heart disease, normal measured fasting glucose and lipids and ECG). ***Many were perimenopausal who sought information but were ineligible for that study***, further illustrating the demand for a perimenopausal VMS study.

CeMCOR has a history of excellent recruitment: 120 women contacted us the first day of a study needing 100 women; 610 premenopausal women not on OC were enrolled and studied for one menstrual cycle within a 16-month time period; and 114 women with PCOS enrolled and were studied within 8 months. Thus, recruitment of the required 175 women is feasible given the geographical and women's media reach of investigators and collaborators and use of internet and social media recruitment strategies.

Approximately 22% of all women in the Metro Vancouver region are in perimenopause and, based on a recent large epidemiological survey, approximately 9% of this population will have severe VMS. Remote participation will offer the opportunity for women living outside the Metro Vancouver area to participate as well. There is a large population of women looking for answers and likely to enroll. CeMCOR and the PI have a history of excellent study recruitment rates, supported by a popular website for laywomen ([www.cemcor.ubc.ca](http://www.cemcor.ubc.ca)) and the publication of several books, including an award-winning book about perimenopause, *Estrogen's Storm Season—stories of perimenopause*.

### 2.13 Compliance/Adherence

The research coordinator will be systematically making contact with and ensuring the well being of each participant monthly during the experimental phase. If adherence or record-keeping problems were anticipated, this should decrease those risks.

A review of adherence in our progesterone for postmenopausal VMS study showed that 98.8% of women used 80% or more of their pills, and the average was 96%. The single individual with poor adherence (42%) discussed her difficulty with the coordinator. Part of our research practice is to reassure women that we all occasionally miss pills, and to record this. This limits the perception that we expect perfect adherence, decreases participant anxiety, and leads to openness about pill taking. Serum progesterone levels could, potentially, be used to confirm adherence.

However, in perimenopause this measurement would be confounded by menstrual cycle timing and progesterone production following ovulation. It is a greater burden to participants and research staff than warranted to obtain a timed progesterone blood sample (at a particular phase of the menstrual cycle) in perimenopause, a life phase characterized by unpredictable and sometimes very long menstrual cycles.

Recent reports of the unreliability of paper-based daily diary methods have come from studies funded by companies who market hand-held electronic record systems. Electronic diary systems are expensive and carry their own issues of training and usability. However, we will be open to developing one should the opportunity arise and funds allow. Our experience over more than 25 years of using daily diary instruments in clinical and research practice is that women are motivated to keep accurate diaries. They often report that the diary-keeping provides valuable insights and helps them understand their new and confusing experiences. The information women gain about their own experience through keeping the Diary or Calendar is, itself, rewarding and encourages study continuation. Our study coordinator emphasizes that the Calendar is important as our primary tool for measuring VMS, and suggests that the woman use it to understand and learn more about herself.

A routine Calendar check after the baseline month and before randomization further ensures data quality. Should there be a problem with diary quality, the research coordinator will individually review items, offer supportive corrective feedback and will ask that the participant keep her record for a further baseline month. All of these strategies are likely to lead to excellent Diary or Calendar quality.

#### **2.14 Likely rate of loss to follow up**

We anticipate that 20-25% of women will discontinue the study following randomization. This figure is based on our experience of those who did not complete our progesterone for postmenopausal VMS study (not including secondary exclusions for abnormal lipids or ECG) in our similar-length trial. The higher figure was for drop-outs during a more demanding (one cycle of daily urinary hormone collection) pilot observational study of perimenopausal VMS.

#### **2.15 How many centres will be involved?**

This is a single-centre study by CeMCOR at Vancouver Coastal Health Research Institute. Given the required sample size, broad inclusion criteria and lack of need for in-person visits, it is feasible to complete this study as a single centre trial; the methodologies and quality assurance measures are all in place. However, given our unexpected recruitment shortfall we have converted it to a single centre Canada-wide trial with remote or in-person options even for locally residing participants.

#### **2.16 Statistical analysis**

The analysis will use analysis of covariance (ANCOVA) of the final outcome variable by therapy assignment, phase of perimenopause (Early/Late) and the interaction of therapy with phase, with baseline outcome variable as a covariate. The interaction term will assess the possibility that the response to therapy differs between those in Early and Late Perimenopause. For Daily Perimenopause Diary or Calendar VMS data, two 28-day (4-week) averages will be compared: immediately prior to therapy assignment and the final 4-weeks of the treatment phase. For questionnaires, the scores from pre-randomization and final visits will be used. The

assumptions of parametric analysis will be checked, and data will be either transformed prior to analysis or analyzed non-parametrically as required.

The primary analysis will be *intent to treat* including all women randomized and taking at least one dose of the experimental/placebo therapies with data carried forward. For practical reasons, only those with at least 14 days of Daily Perimenopause Diary or Calendar data will be included in any diary-based outcome measures (one week of baseline and one week of therapy).

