## **1.2 Principal research question**

**Research Question:** Is progesterone (OMP) an effective treatment for night sweats and hot flushes in perimenopausal women?

1. Is daily OMP therapy (300 mg, taken before sleep) an effective therapy for hot flushes and night sweats (vasomotor symptoms, VMS) in Early and Late Perimenopause?
2. Does OMP therapy improve other perimenopausal symptoms, specifically sleep disturbances and anxiety?

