### 2.3 Allocation of participants within the trial

Random allocation will be stratified by phase of perimenopause (Early, <60 days cycle length, versus Late, having had at least one  $\geq 60$  day long menstrual cycle). Two lists of random numbers will be computer-generated by a statistician not associated directly with the study. Permuted blocks of size 10 will be used. A research pharmacist will access appropriate (Early or Late Perimenopause) lists from this computer webpage to determine whether to dispense Experimental or Control therapy.

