### **2.17 Frequency of analyses**

There will be a single primary analysis when all data are entered into a database and checked for completeness and accuracy. However, our sample size calculations were based on the assumption that the SD for within-woman change during perimenopause will be 20% greater than that in menopause. Through the Data Safety and Monitoring Committee, an interim analysis when we have sufficient data for comprehensive assessment, will confirm whether this assumption was accurate; if necessary, we will increase our enrollment target to ensure we have 80% power.

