**Re: Randomized Controlled Trial of Progesterone for Perimenopausal Vasomotor Symptoms**

As Chair of the Clinical Research Ethics Board (CREB) at the University of British Columbia (UBC) that has overseen and approved the Canadian Institutes for Health Research-funded Randomized Controlled Trial of Progesterone for Perimenopausal Vasomotor Symptoms (VMS) since it began in 2011, I have reviewed the posted protocol, which was the latest one approved by CREB and the evidence that it has some inadvertent clerical omissions. I have also reviewed the proposed Amendments to this protocol.

The protocol omissions include this study's Data Safety and Monitoring Committee decision (and details about the blinded analysis leading to it) that led to the official increase in sample size. Another was that the DSMC mandated addition of the Personal Health Questionnaire-9 (PHQ-9) to screen for depression. The investigators then decided (and CREB approved) administration of the PHQ-9 also at the study end. However, the analysis of PHQ-9 was inadvertently not listed as a secondary outcome. And finally other instruments were included in the study initially for administration at the randomization and the final study visits, were approved by CREB, were partially described in the protocol but not were listed as secondary outcomes including: a likert-type assessment of "Women's Perception of Change" (related to daytime hot flushes and night sweats, flow and sleep) and the CeMCOR Perimenopause Interference Questionnaire (CeMCOR PIQ).

Although it is unusual to amend a RCT protocol once the database has been locked and statistical analysis has occurred, these amendments to the protocol are important, and they will allow the outcomes of approved, collected instruments to contribute to the scientific literature. To collect data that, for inadvertent clerical reasons cannot be evaluated and reported, would be unethical given the overall "contract" that participants make with investigators and institutions. Participants expect that what they have contributed will add to Knowledge with an expectation of providing benefit for Society or Science.

For these reasons, I approve uploading of Amendments dated November 9, 2018 to the 2014 posted protocol.

All the best,

[name]

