## **Amendment #4 (PRIMARY OUTCOME)**

We will also do subgroup analyses of VMS Score by Early Perimenopause (no skipped period or <60 day cycle length) and by Late Perimenopause (those with skipped or ≥60 day cycle lengths).

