### **Amendment #6 (2.11 Sample size)**

A pre-planned evaluation of sample size was undertaken after 68 women had completed the study. This involved evaluation of the SD of the VMS Score in the final month without regard to random study group assignment. An **effective standard deviation (SD) of ~ 9** in the Vasomotor Symptom Score SD over the last 4 weeks of experimental therapy was discovered after adjustment for the fact that the final and the run-in SD values correlated with an r of 0.56. This interim assessment was blinded and without knowledge of the therapy. The original estimated SD of 6.25 was used in our application to CIHR. This re-evaluation of sample size led to an increased enrolment of goal of 245.

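### The only ANCOVA includes therapy by phase but does not say how Early and Late are weighted in the primary therapy test; with equal weights, planned power holds only if the two phases are of similar size

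*Combined protocol and SAP*

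**What the plan says.** - **Model (section 2.16).** The final outcome is analysed by ANCOVA on therapy, "phase of perimenopause (Early/Late) and the interaction of therapy with phase, with baseline outcome variable as a covariate". The interaction has a stated purpose: to see whether response differs by phase. Nothing is said about phase weights, coding or type of sum of squares for the therapy term.
- **Sample size (section 2.11).** 175 women, effect size 0.48, two-tailed alpha 0.05, 20% discontinuation, "having a power of 0.80 to detect a significant difference between two groups". Phase and interaction play no part in the calculation.
- **Amended size (Amendments #1 and #6).** The target rises to 245, using an effective SD of about 9 "after adjustment for the fact that the final and the run-in SD values correlated with an r of 0.56".
- **Randomisation (section 2.3).** "Random allocation will be stratified by phase of perimenopause", in blocks of 10. This balances the arms within each phase, not the sizes of the phases. No expected split, cap or quota is given anywhere.
- **Question (section 1.2).** Whether daily progesterone is "an effective therapy for hot flushes and night sweats (vasomotor symptoms, VMS) in Early and Late Perimenopause".
- **Subgroups (Amendment #4).** "We will also do subgroup analyses of VMS Score by Early Perimenopause", and likewise for Late. No primary contrast is named.
- **Timing (ethics board letter, November 2018).** The amendments came "once the database has been locked and statistical analysis has occurred".

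**The concern.** Once therapy by phase is in the model, there is no single therapy effect until the two phase effects are given weights. Weighting by phase size gives the overall phase-adjusted difference, which matches the two-group calculation in section 2.11. Weighting equally gives the simple mean of the Early and Late effects, so a small phase counts as much as a large one. Both can be obtained from the model as written, and they can give different p-values.

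Stratified allocation does not prevent this. If recruitment produces mostly one phase, the equal-weighted test leans on the small phase, its standard error grows, and the power bought by raising enrolment from 175 to 245 can be partly lost.

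**Working it through.** **1. Reproduce the plan's figures** (two-sample t-test, noncentral t, two-sided alpha 0.05, power 0.80).

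- Section 2.11: d = 3/6.25 = 0.48 gives 70 per arm, or 140; 140/0.80 = 175. Reproduced.
- Amendment #6: 9 × sqrt(1 - 0.56²) = 7.456; d = 3/7.456 = 0.402, which gives 98 per arm, or 196; 196/0.80 = 245. Reproduced.

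The 245 comes out only if the gain from r = 0.56 is applied to the SD of 9, so the amended target has already spent the benefit of baseline adjustment.

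**2. Variance of the two contrasts.** Let N be the number analysed, p the smaller phase's share, σ the baseline-adjusted SD, with 1:1 allocation within phase. The phase effects have variances 4σ²/(Np) and 4σ²/(N(1-p)).

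- Size-weighted: p² × 4σ²/(Np) + (1-p)² × 4σ²/(N(1-p)) = 4σ²/N, the same as the two-group comparison.
- Equal-weighted: ¼ × [4σ²/(Np) + 4σ²/(N(1-p))] = σ²/(Np(1-p)).
- Ratio of equal-weighted to size-weighted: 1/(4p(1-p)).

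**3. Power of the equal-weighted test, same effect (3 points) in both phases.** Noncentral t with N - 5 degrees of freedom, d = 0.402. The split is an assumption shown as a range, because the documents give none.

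| Split | Variance ratio | 196 analysed | 245 analysed, full effect | Enrolment for 0.80 (analysed/0.80) |
|---|---|---|---|---|
| 50/50 | 1.00 | 0.80 | 0.88 | 245 |
| 60/40 | 1.04 | 0.78 | 0.87 | 256 |
| 70/30 | 1.19 | 0.73 | 0.82 | 292 |
| 75/25 | 1.33 | 0.68 | 0.78 | 327 |
| 80/20 | 1.56 | 0.61 | 0.71 | 383 |

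The 196 column follows the plan's own accounting, with 20% lost. The 245 column supposes that carry-forward keeps every woman at the full effect. Between the two, if the 20% carried forward show half the effect, the mean effect is 3 × (0.8 + 0.2 × 0.5) = 2.7 and power at 70/30 with 245 analysed is 0.73.

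The design before the increase behaves the same way (140 analysed, d = 0.48): 0.80, 0.79, 0.73 and 0.62 at 50/50, 60/40, 70/30 and 80/20.

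**4. Power of therapy + phase + baseline.** 0.80 with 196 analysed, whatever the split. Simulation (4,000 trials per split, 196 women, r = 0.56) at 50/50, 60/40, 70/30 and 80/20 gave 0.80, 0.81, 0.80 and 0.80 for this model, against 0.80, 0.79, 0.72 and 0.61 for the equal-weighted test.

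**5. Unequal effects.** Take 70/30, an overall effect of 3 and 196 analysed.

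- Smaller phase 5: larger phase (3 - 0.3 × 5)/0.7 = 2.14, equal-weighted mean 3.57, power 0.86.
- Smaller phase 2: larger phase (3 - 0.3 × 2)/0.7 = 3.43, equal-weighted mean 2.71, power 0.64.

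The equal-weighted test can therefore gain or lose power when the effects differ.

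**The case against.** The strongest reply is that the loss rests on two things the documents do not state: equal weighting and an uneven split. Section 2.11 speaks of a difference between two groups, and section 2.16 gives the interaction its own job, so the therapy term was probably meant as the overall comparison. This stands as a limit on the claim: a loss of power is possible, not shown. It does not close the gap, because the model as written does not deliver that overall contrast until the weights are stated.

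Equal weighting is also a legitimate answer to section 1.2, which asks about both phases. With a common effect the two contrasts estimate the same quantity and differ only in precision. That is correct. The difference in precision is the point, since the sample size made no allowance for it.

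The 196 ignores carried-forward data, which section 2.16 includes. This is fair and can help materially, hence the second power column. It does not rescue 80/20.

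The interaction was prespecified, whereas Amendment #4 came after analysis. So the interaction test should be kept, and Amendment #4 does not replace it.

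Three stronger readings are tempting but not supported:

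- **A sequential test.** From the order of terms in section 2.16, a reader might infer that therapy is tested before baseline is fitted, with an inflated false-positive rate. The section lists terms, not a fitting order. Sections 2.8 and 2.16 both make baseline a covariate, and Amendment #6 adjusts the SD for it.
- **A promise of one contrast.** Section 2.17 says "There will be a single primary analysis when all data are entered into a database". In context this sets the final analysis against the interim check of the SD; it does not promise a single contrast.
- **A one-phase coefficient.** Reference-cell coding would make the therapy coefficient the effect in one phase only. Nothing in the plan suggests that this was intended.

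**Conclusion.** The point holds as an unspecified weighting in the primary therapy test, with a conditional cost. If the test is equal-weighted and the effect is common to both phases, the loss is nil at 50/50 and under 2 percentage points at 60/40. At 70/30 it is about 7 points and at 80/20 about 19 points, with 196 analysed. If all 245 are analysed at full effect, power stays above 0.80 at 70/30 and falls to 0.71 at 80/20.

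This rests on a difference of 3, an adjusted SD of 7.456 (the reading that reproduces 245) and an assumed range of splits. If 9 is itself the adjusted SD, d = 3/9 = 0.333 and even the overall comparison has power of about 0.64 with 196 analysed; that is a separate sample-size question. A reader should not conclude that the trial did lose power, or that its primary p-value is invalid. The documents show neither. The point is worth acting on because the remedy is cheap and removes the dependence of power on the split.

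**What to change.** Take the primary therapy effect from:

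final 28-day mean VMS Score = therapy + phase (randomisation stratum) + baseline 28-day mean VMS Score.

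Keep the prespecified therapy by phase test in a second, supportive model, and report the Early and Late estimates with 95% confidence intervals.

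Because analysis had already taken place when the amendments were approved, this cannot be presented as prespecified. The report should say which contrast and phase weights gave the primary p-value. If it was not the contrast above, add that contrast as a labelled post hoc sensitivity analysis and leave the primary result in place.

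The cost is one extra model fit and a sentence or two, with no new data. The downside is that the interaction moves to a supportive model and any added result is post hoc.
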